6 STUDY SETTING

This is a multicentre study and will take place in two sites including the tertiary NICUs at St Michaels Hospital and the Southmead Hospital. We look after, on average, 65 cooled infants each year between the two NICUs. This will give adequate numbers of cooled infants and parents who could be

Date 11.02.2020 Version 1.6

24 of 37

IRAS No. 257430 CoolCuddle protocol

potentially recruited for the study. The inborn infants will be identified by the staff in the neonatal unit and will inform the research nurse. Infants with HIE born in the peripheral hospitals will be transferred by the dedicated neonatal transport team to St Michael's and Southmead NICU. The neonatal transport team will inform the research nurse about the baby. A short parent information sheet will be available in the peripheral hospitals and the neonatal transport team for the staff to give to the parents. The research nurse or the principal investigators and GCP compliant colleagues at St Michaels and Southmead Hospitals will approach the parents of infants undergoing cooling therapy to inform them about the study and recruit the families into the CoolCuddle study after getting the informed consent.

7 SAMPLE AND RECRUITMENT

7.1 Eligibility Criteria

The cooled infants admitted to the NICUs of St Michael's and Southmead Hospital and their parents between Sept 2019 and Jan 2021.

7.1.1 Inclusion criteria

- Newborn infants born at gestation ≥ 36+0 weeks
- undergoing whole-body cooling for hypoxic-ischemic encephalopathy as per the national and south west neonatal network cooling therapy pathway and their parents who consent to participate in the study.
- cooling provided by a cooling device offering servo-controlled cooling using a wrap or blanket covering the whole body.
- receiving intensive care and will have probes monitoring core temperature and scalp EEG electrodes, may have central or peripheral arterial or venous catheter and may have a urinary catheter.

7.1.2 Exclusion criteria

Any of the following in a cooled infant at the time of screening

- 1. needing fraction of inspired oxygen (FiO2) >70%
- 2. receiving high-frequency oscillatory ventilation
- 3. requiring a mean airway pressure > 12cm H2O
- 4. receiving inhaled nitric oxide for persistent pulmonary hypertension
- 5. > 1 chest drain inserted for pneumothorax

- 6. receiving three or more inotrope infusions
- 7. Congenital anomalies such as hydrops fetalis and congenital diaphragmatic hernia
- 8. Non-English speaking parents
- 9. If potential participants are involved in another intervention study, an eligibility check to participate in the "CoolCuddle" study will be needed before recruitment.
- 10. If a baby excluded during the initial screening because of criteria 1 to 6, becomes eligible later during the cooling period due to resolution of those criteria, the baby can be screened again for participation in the study.

7.2 Sampling

In 2017, 69 cooled infants were admitted between St Michael's and Southmead NICU. Seven infants would have been excluded leaving 62 potentially eligible infants. With this projected number of potential infants in 2019, we anticipate being able to enrol our target of 24 infants over 12 months (39% recruitment rate).

7.2.1 Size of sample

The sample size chosen is pragmatically based on a conservative estimate of the number of parents we believe will consent to this process in the time available.

Stage 1 (Iterative refinement): 4-6 cooled parents-infant pairs over 3 months (Fig 1).

Stage 2 (main data set): 20-24 cooled parents-infant pairs over 12 months (Fig 1).

7.2.2 Sampling technique

We will use a purposive sampling strategy and approach sequentially all the parents of babies admitted for cooling therapy at the St Michael's Hospital or Southmead Hospital NICU. Depending on staff availability, we may not be able to recruit families if two or more infants are admitted for cooling therapy simultaneously.

7.3 Recruitment

7.3.1 Sample identification

Potential participants will be identified by medical or nursing team at both St Michael's and Southmead NICUs. The transport team retrieving babies to both the NICUs will also identify the outlying patients and inform the research team. All parents will receive the participant information sheet from the medical team looking after the baby and/or the research team looking after the baby. For families who are unlikely to visit the baby in the recruiting sites within 24hours of age, the research team will obtain

consent over telephone and reconfirm the consent when the parents visit their baby. When two babies receive cooling therapy at the same time in a recruiting site, we will recruit the families in a staggered manner so that the "CoolCuddle" episodes are offered and undertaken at convenient separate time points and they do not overlap. Regular newsletters and study days will be conducted to remind the clinical team of the study. Details of the study including the research question, inclusion and exclusion criteria of the participants will be placed on the notice board in both NICUs.

7.3.2 Consent

We will invite both parents with an eligible baby to take part. From those who agree we will obtain informed consent during the cooling period (72 hours from the initiation of active cooling) from the parent with parental responsibility (mother for unmarried parents, mother or father for married parents) for the baby and the parent to participate in the "CoolCuddle" and the other parent if they will be willing to participate in the "CoolCuddle". If one parent is willing and the other parent does not wish to participate in the "CoolCuddle", we will offer "CoolCuddle" to the parent consenting to participate in the study as long as the parent with parental responsibility provides consent for the baby to participate in the "CoolCuddle". In same sex marriage, we will seek consent from the birth mother or the other parent if they are married. Stage 1 of the study requires the participants to contribute to improving the cuddling process by vocalising their thoughts.

7.4 Discontinuation / withdrawal of Participants from Study

Parents will have the right to withdraw their infant from the study at any time. Parents who wish to discontinue with the study intervention will be asked for permission for the study team to complete data collection and follow up. They may withdraw consent for any aspect of the study including future procedures and data collection. In addition, the treating clinician may discontinue a participant from the study at any time if they consider it to be in the best interests of the infant's health and wellbeing. Researchers will withdraw a participant from the study, if the infant after recruitment was unable to undergo at least one cuddling episode due to fulfilling an exclusion criterion or parental reasons. Parents who have consented to both themselves and their infant's participation will be able to withdraw either or both consent.

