In stage 2, we will test the impact of the "CoolCuddle" protocol on the stability of cooling process, intensive care support including support for breathing, heart function and brain activity monitoring, and whether there are any adverse effects. This will be undertaken in 20-24 parents - infant pairs over a period of 12 months. Each infant will have a minimum of one cuddle with their parents. We will compare the physiology data between the pre, during and post cuddle to assess the short-term safety of cuddling babies during cooling. These data will tackle the concerns of the neonatal community regarding the short-term safety of cuddling the babies during cooling by reporting any safety issues including any adverse or serious adverse events. To address the issue of long-term impact of cuddling the babies undergoing cooling therapy, as parent-infant bonding has been shown to be improved with early parent-infant interaction in non-cooled babies, we will measure the maternal mood and parent-infant bonding using validated questionnaires around discharge and when the baby is 8 weeks of age.

Given that the early parent infant interaction including cuddling is the standard care for babies receiving intensive care in the NICU, we will adopt a traffic light system in stage 3 to progress with the findings of stage 2.

Green zone: If there are no adverse effects with the "CoolCuddle" protocol, we will integrate the "CoolCuddle" protocol into the existing cooling therapy pathway at the study centres. The modified "CoolCuddle" protocol including the steps of the "CoolCuddle" process and a data collection tool comprising adverse events and bonding questionnaires will be published on the southwest neonatal network website. We will consider appropriate further methods of investigation to confirm the short and long-term safety in larger sample sizes or rolling out the "CoolCuddle" study to other networks with collection of safety data and bonding scores with further potential funding.

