Orange zone: If modifiable adverse events or adverse physiological changes or resolvable issues from parents or healthcare staff persist at the end of the study, we will modify the "CoolCuddle" protocol taking these issues into account. We will explore if there is a specific subgroup of cooled infants where the "CoolCuddle" might not be suitable . We will discuss with the steering committee whether further funding is needed to test the protocol or whether we can proceed as outlined in the green zone.

Red zone: If there are unmodifiable adverse effects at the end of the research, we will abandon the implementation and publish our findings.

During stage 3, we will complete the NIHR report, prepare the manuscript for publication and disseminate the findings.

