4.2 Outcomes

- Difference in mean/median and variability of surface and core temperature, ventilation, cardiovascular and neurophysiology parameters between the pre-cuddle, "CoolCuddle" and post cuddle epochs.
 - Day of life when oral feeds established
 - Mode and type of feeding at discharge and 8 weeks
 - Maternal mood assessed using Edinburgh postnatal depression scale¹ when the baby is 5-7 days of age and at 8 weeks.
 - Maternal-infant bonding assessed using Mother-infant bonding score³ when the baby is 5-7 days of age and at 8 weeks.
 - Father-infant attachment assessed using paternal postnatal attachment scale² at 8 weeks
 - Qualitative feedback on the "CoolCuddle" protocol
 - Incidence of adverse events including frequency of administering stop rules for "CoolCuddle", and dislodgement of endotracheal tube, central or peripheral arterial catheter, central venous catheter

5.STUDY DESIGN, METHODS OF DATA COLLECTION AND DATA ANALYSIS

This study will be a cohort study involving a controlled trial without randomisation design recruiting the cooled infants admitted to the NICUs of St Michael's and Southmead Hospital and their parents between September 2019 and January 2021.

5.1 Stage 1: Developing "CoolCuddle" protocol by refining existing cuddling technique using an iterative process (3 months)

Over 3 months, we will use the current family centred cuddling technique that we use for non-cooled babies receiving intensive care for babies receiving cooling treatment on 4-6 parents-infant pairs. We will attempt a minimum of one cuddle session per family up to 2 hours in length. We will refine the protocol by using 'talk-aloud' qualitative methods during each of the "CoolCuddle" sessions. Talk-aloud methods are used to gather data on usability and development of products and tasks³⁴. Talk-aloud methods involve participants describing their actions and how they go about completing the task. The audio-recordings made are used to improve the process through insights and modifications that arise during the session. A member of the research team will also observe all the "CoolCuddle" sessions and make field notes of changes made and actions taken.

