5.1.1 Cuddle technique

We will postpone the cuddle if the baby has any exclusion criterion before any cuddling episode. (section 7.12) If the baby has status epilepticus, we will post pone the cuddling episode until the status epilepticus is resolved.

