The physiology data collection will be similar to stage 1; frequency and duration of data collection will be informed by the learning from the stage 1. The physiology data will be collected in the CRF and stored in the electronic databases. The questionnaire data including the responses from the EPDS, MIBS and paternal postnatal attachment scale will be stored in a REDCap database.

Data including the reasons parents did not want to consent for the study or cut short the cuddling episodes will be recorded.

The qualitative interviews will be audio-recorded, transcribed and anonymised.

Data Analysis

We will use descriptive statistics to report the parental questionnaire data and the adverse events. We will measure the mean or median (as appropriate) for the main physiological measures (see above). We will undertake three pairwise comparisons of pre-cuddle versus during-cuddle, during-cuddle versus post-cuddle and pre-cuddle versus post-cuddle using parametric t test or non-parametric Wilcoxon tests depending on the data distribution. We will derive the differences between the three

Date 11.02.2020 Version 1.6

23 of 37

IRAS No. 257430 CoolCuddle protocol

epochs (pre-cuddle, cuddle, and post-cuddle) and identify the magnitude of the differences, or variability which occurs. Using multilevel mixed-effects linear regression models, using data clustered by infant (or cuddle), we will assess if any difference in measures is likely to be due to chance (using a conventional level of statistical significance of p<0.05). We will also explore continuous monitoring of the physiological measures to establish variability over longer periods and the potential for adverse events. All data analysis will be conducted using the software SPSS or STATA.

We will compare our findings from the parental questionnaires with normative data. To compare parental bonding, we will collect these scores in our study to ensure they are in the satisfactory range following the "CoolCuddle". There are published normative data for mother-infant bonding scores³ and cut-offs for the father-infant attachment scores². We will compare our scores against these published data. We will also have detailed audit data on breastfeeding initiation and duration before September 2019 to compare with our study findings. If the cuddling process is stopped this will be treated as an adverse event and fully investigated to realise whether the problem is endemic, or modifiable and preventable.

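### Consented infants who never have a cuddle are withdrawn with no stated denominator or follow-up, so receipt of a cuddle is 100% by construction and the parent outcomes describe a selected group

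*Protocol*

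**What the plan says.** Protocol section 7.4 (Discontinuation / withdrawal) contains the rule: "Researchers will withdraw a participant from the study, if the infant after recruitment was unable to undergo at least one cuddling episode". It names two triggers: the infant meets one of the criteria for exclusion, or the reason lies with the parents. The action is taken by the researchers, after consent, and is not optional. The same section treats parents who choose to stop the intervention differently: "Parents who wish to discontinue with the study intervention will be asked for permission for the study team to complete data collection and follow up". No such request is attached to withdrawal by the researchers.

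Other parts of the protocol bear on the rule:

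- Section 5.1.1 makes instability a reason to wait first: "We will postpone the cuddle if the baby has any exclusion criterion before any cuddling episode". Withdrawal follows only if no cuddle ever takes place.
- Section 3 says of Stage 2: "Each infant will have a minimum of one cuddle with their parents". Sections 7.2 and 7.2.1 set the Stage 2 size at 20–24 pairs. They do not say whether a withdrawn infant counts towards that number or is replaced.
- The Stage 2 data collection text records why parents refused consent and why they shortened a cuddle. It does not mention families who consented and then never cuddled.
- Section 4.2 lists maternal mood, maternal bonding, father's attachment and feeding as outcomes. The Stage 2 data analysis text compares the bonding and attachment scores with published norms or cut-offs, and breastfeeding with audit data from before September 2019.

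**The concern.** The overall aim in section 4 is to put the procedure into the existing cooling pathway. A unit considering adoption will ask for what share of families who agreed a cuddle could be delivered, and why it failed in the rest. Under section 7.4 the families who would answer that leave the study, and no statement ensures that they are even counted.

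Consent without a cuddle is foreseeable. Sections 7.3.1 and 7.3.2 allow consent at any time in the 72-hour cooling period, including by telephone before the parents reach the unit. An infant may then stay too unwell, or the parents may not go ahead, until the cooling and rewarming window closes.

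The parent outcomes are also affected. There is no concurrent comparison group, so these results rest on comparison with outside figures. Leaving out families whose infant stayed too ill, or who decided against holding the baby, could plausibly make the scores and feeding rates look better. An analysis plan can define populations, but it cannot recover 8-week questionnaires that were never sought because the family had been withdrawn.

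**Working it through.** **The plan's own figure.** Section 7.2 gives 69 cooled infants in 2017, 7 of whom would have been excluded, and a target of 24. 69 − 7 = 62 and 24/62 = 38.7%, which agrees with the stated 39%. The sample size is pragmatic, so there is no power calculation to reproduce.

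**What the rule fixes.** Let c be the infants cuddled at least once and w the consented infants never cuddled. Delivery among consented infants is c/(c + w). Withdrawing the w infants turns this into c/c = 1 for any w.

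**Size.** The protocol gives no value for w, so w is an assumption and a range is shown. Intervals are exact (Clopper–Pearson): with x = c and n = c + w, the lower limit is the 2.5% point of Beta(x, n − x + 1) and the upper limit the 97.5% point of Beta(x + 1, n − x).

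| Never cuddled (assumed) | Cuddled/consented | Per cent | Exact 95% CI |
|---|---|---|---|
| any number, under the rule | 24/24 | 100 | 85.8–100 |
| 2 | 24/26 | 92.3 | 74.9–99.1 |
| 3 | 24/27 | 88.9 | 70.8–97.6 |
| 4 | 24/28 | 85.7 | 67.3–96.0 |
| 6 | 24/30 | 80.0 | 61.4–92.3 |
| 8 | 24/32 | 75.0 | 56.6–88.5 |

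At the lower target, 20/20 has an interval of 83.2–100%. With 4 never cuddled, 20/24 = 83.3% (62.6–95.3%).

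**Parent outcomes.** Let p = w/(c + w), and let D be the difference in mean score, never-cuddled minus cuddled families. The mean over all consented families is the cuddled mean plus p × D. With w = 3, p = 3/27 = 0.11; with w = 6, p = 6/30 = 0.20. The cuddled-only mean is therefore off by 11% or 20% of D. The protocol gives nothing from which to estimate D, so only the multiplier can be stated.

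**What the 20–24 counts.** If 24 means cuddled infants, the consents needed are 24/(1 − d), where d is the share never cuddled: 27 at 10%, 30 at 20% and 35 at 30%. If 24 means consented infants, the number cuddled is 24(1 − d): about 21.6 at 10% and 19.2 at 20%, the latter below the stated lower bound of 20.

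**What the rule does not fix.** Stop-rule events remain free to occur among cuddled infants. If 2 of 24 had a cuddle stopped, 22/24 = 91.7% would be free of a stop; if 4 did, 20/24 = 83.3%.

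**The case against.** The strongest reply is that the rule does little harm to what the study mainly measures. The main quantitative outcome compares epochs before, during and after the cuddle within the same infant, and the events of interest are those during the cuddle. An infant never cuddled has no such epochs and cannot contribute under any rule. This stands: for these results the loss narrows the population described but does not bias the contrast.

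A reader might infer that tolerability is 100% by construction. The protocol does not support this. Section 4.2 makes the frequency of stop rules an outcome, and the Stage 2 data analysis text says "If the cuddling process is stopped this will be treated as an adverse event and fully investigated". Only receipt of a first cuddle is fixed. Nor is a feasibility or uptake rate a listed outcome, so no planned statistic is forced to 100%; the loss is of a figure that the study should be able to give.

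A reader might also infer that the rule removes the group to be examined in the Orange zone of section 3: "We will explore if there is a specific subgroup of cooled infants where the" procedure might not suit. That zone is triggered by problems that persist at the end of the study, and its main evidence is how cuddled infants responded. The rule does not remove that evidence.

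Three further points narrow the concern:

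- Postponement, and rescreening of infants first excluded, mean that only families who never cuddle in the whole window are lost.
- Reasons for refusal and for shortened cuddles are recorded, so reluctance is partly captured.
- The sentence on parents who discontinue the intervention does not require a previous cuddle. Some families withdrawn for parental reasons might be asked to stay in follow-up under it. The two sentences overlap without saying which prevails, and the permission sentence does not cover an infant who stayed too ill.

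Finally, analysis populations are commonly left to an analysis plan, and describing families who cuddled is a legitimate aim. Both are true, but the withdrawal is a conduct rule that stops data collection, and describing cuddled families does not require dropping the others.

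**Conclusion.** The concern holds in a limited form. Section 7.4 withdraws consented infants who never have a cuddle, and the protocol states neither a denominator nor follow-up for them. Receipt of a cuddle is then 100% among retained infants by construction, and the mood, bonding, attachment and feeding results describe families selected for having cuddled.

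The size depends on a number that the protocol does not give. Between 2 and 8 never-cuddled infants beside 24 cuddled would put delivery at 92% down to 75%, where the rule yields 24/24. A favourable shift in the parent outcomes is plausible but not demonstrated, because its size depends on an unknown difference between the two groups of families. The point does not reach tolerability during a cuddle, the within-infant physiology contrast or the during-cuddle event counts, beyond the population to which they apply.

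**What to change.** In section 7.4, replace the withdrawal rule with retention of every consented family unless the parents withdraw consent. This concerns study data only and changes nothing about when a cuddle is offered, postponed or stopped. Then:

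- Record the reason that no cuddle took place.
- Report cuddled out of consented infants with an exact 95% confidence interval.
- Seek permission from never-cuddled families for feeding data and for the day 5–7 and 8-week questionnaires. Report parent outcomes for all consented families alongside the cuddled subset.
- Label the physiology and cuddle-event analyses as applying to cuddled infants.
- State in sections 7.2 and 7.2.1 whether the 20–24 counts cuddled or consented infants.

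The cost is protocol wording and a few extra questionnaires from families who have already consented. The delivery figure may look slightly less favourable. Some never-cuddled families will decline the questionnaires, so the numbers who returned them should be given.
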